### 8.8.3 Analyses of Tertiary Endpoints

Analyses of the tertiary efficacy endpoints will follow the same methods as the primary analysis of the primary endpoint unless otherwise stated. No sensitivity analysis will be performed for tertiary efficacy endpoints.

Tertiary efficacy endpoints include the following:

- Upper Extremity Composite and Lower Extremity Composite Percent Predicted: The percent predicted total force values will be determined based on reference equations adjusting for age, gender, height, and weight (APPENDIX 10.2). The percent predicted force will be calculated for each side and the bilateral percent predicted values will be

averaged for each upper extremity muscle group. The mean of the four averages in percent predicted scores will be calculated to create a percent predicted UEC score for each subject, and analyzed relative to baseline to create a UEC mean change in percent predicted score. Similar methodology will be used to determine the percent predicted total force values for the LEC. Summary statistics on the changes from baseline will only be presented.

- Muscle Strength Total Force (kg) and Percent Predicted in Each Individual Muscle Group: Bilateral total force and percent predicted total force for each individual muscle group included in the UEC and LEC and percent predicted for the knee extensors will be reported. Summary statistics on the changes from baseline will only be presented.
- Total Score on the GNEM-FAS
- Self-Care Domain Score on the GNEM-FAS
- Individual Neuromuscular Quality of Life Questionnaire: The individual domain scores, a 45-item self-report questionnaire on the impact of key muscle disease symptoms on the ability to perform basic activities of daily living, functional independence, relationships and overall well-being will be recorded.
- Clinical Global Impression Scale: Investigator assessment of severity of subject's GNEM using the CGI-Severity scale (CGI-S) and improvement (CGI-I) during treatment. Physicians caring for each subject will provide a global assessment of change using a seven point scale ranging from 1 (normal) to 7 (extremely affected) for CGI-S at Baseline and -3 (severe worsening) to +3 (significant improvement) for CGI-I at Week 24 and Week 48. Descriptive statistics and number and percentage of subjects will be reported for CGI-S. The CGI-I score will be analyzed using GEE as well as a shift table conditional on the CGI-S categories at baseline.

No adjustment for multiplicity will be performed for these endpoints. Each endpoint will be tested at the 0.05 two sided level of significance and nominal p-values will be reported.

#### 8.8.4 Analyses of Sialic Acid, Creatine Kinase and Free ManNAc

The following clinical lab outcomes will be analyzed using GEE using the SA analysis set. No imputation will be performed for missing data. Free, total, and bound urine SA and urine ManNAc are collected at Baseline, Week 24, and Week 48. All other labs are collected every 8 weeks up to Week 48.

- Free SA: Free SA levels in serum assess the drug concentration in the bloodstream resulting from treatment and are the best indicator of compliance with the treatment regimen. Free SA levels in serum are expressed in micrograms of SA per ml of serum
- Free SA in urine: Free SA levels in urine will be assessed to determine the overall absorption of SA-ER over time. Free SA levels in urine will be expressed in micrograms of SA per ml of urine.

- Total SA in urine: Total SA levels in urine will be assessed to determine the accumulated excretion of sialic acid from dosing. Total SA levels in urine will be expressed in micrograms of SA per ml of urine.
- Bound Sialic Acid in urine: Bound SA levels in urine is calculated as the difference between each subject's total sialic acid and free sialic acid in urine corrected for total protein. Bound sialic acid in urine may also be corrected for creatine and calculated as the difference between each subject's total sialic acid and free sialic acid corrected for creatine. The primary correction for SA will be total protein with creatine correction only used when an alternate method is required
- Creatine Kinase Levels: CK levels in serum will be measured to assess the degree of reduction of CK levels observed as a surrogate for muscle injury.
- Free ManNAc in urine: Free ManNAc levels in urine will be assessed to determine the amount of naturally occurring ManNAc in the urine of study subjects and the stability of these levels over time. Free ManNAc levels in urine will be expressed in micrograms of SA per ml of urine. Changes from baseline in Free ManNAc levels in urine will be analyzed.
- Free ManNAc/Free SA in urine: The ratio of free ManNAc to free SA levels in urine will be assessed to ensure compliance with the restriction placed on ManNAc consumption during the study period.

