7.5.3 Drug Concentration Measurements

The concentration of free SA in serum will be measured. At the Baseline Visit and each subsequent visit a serum sample will be collected prior to the morning dose of study medication (pre-dose) to assess trough levels of free SA.

The free, total, and bound urine SA levels (corrected for creatinine) will be measured. At the Baseline, and Week 16, 32, and 48 (or Early Termination) visits, first-morning void urine will be collected (pre-dose) to assess trough levels; the volume obtained will be recorded.

Collection and processing instructions can be found in the Laboratory Manual.

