7.5.5.6 Clinical Laboratory Tests for Safety

The clinical laboratory evaluations to be performed in this study include a serum chemistry, complete blood count (hematology), and urinalysis; specific analytes are listed in [Table 7.5.5.6.1](#). Clinical laboratory testing will be performed at every visit. Blood and urine samples will be collected prior to administration of study drug; fasting is not required. Refer to the Laboratory Manual for additional details.

Table 7.5.5.6.1: Clinical Laboratory Assessments for Safety

Chemistry	Hematology	Urinalysis
Alanine aminotransferase (ALT)	Hematocrit	Appearance
Alkaline phosphatase	Hemoglobin	Bilirubin
Amylase	Mean corpuscular hemoglobin (MCH)	Blood pH
Aspartate aminotransferase (AST)	MCH concentration (MCHC)	Color
Bilirubin (direct and total)	Mean corpuscular volume (MCV)	Creatinine ²
Blood urea nitrogen (BUN)	Platelet count	Glucose
Calcium	Red blood cell (RBC) count	Hemoglobin
Chloride	Reticulocyte count	Ketones
Cholesterol (total)	Neutrophil count (absolute and %)	Leukocyte Esterase
Creatine kinase ¹	Lymphocyte count (absolute and %)	ManNAc ³
Creatinine	Monocyte count (absolute and %)	Nitrite
Gamma-glutamyl transpeptidase (GGT)	Eosinophil count (absolute and %)	Protein
Glucose	Basophil count (absolute and %)	Specific gravity
Lactate dehydrogenase (LDH)	White blood cell (WBC) count	Urobilinogen
Lipase	WBC differential	
Phosphorus		Pregnancy test (if applicable)
Potassium		
Protein (albumin and total)		*Special assessment
Sodium		Serum pregnancy test if a positive urine pregnancy test
Triglycerides		

¹ Also designated as PD variable (Section 7.5.2.9)

² Relevant to Drug Concentration Measurements (Section 7.5.3)

³ To screen for use of prohibited medications (Section 7.4.6.1)

If urinalysis detects protein, leukocyte esterase, blood or nitrite, microscopic examination will be conducted. The microscopic examination will consist of White Blood Cell (WBC), Red Blood Cell (RBC), Epithelial Cells: Squamous, Epithelial Cells: Transitional, Epithelial Cells: Renal Tubular, Hyaline Casts, WBC Casts, RBC Casts, Waxy Casts, Granular Casts, Calcium Oxalate Crystals, Uric Acid Crystals, Triphosphate Crystals, Yeast, Bacteria, Amorphous Urates, and Amorphous Phosphates.

Subjects who experience a SAE possibly or probably related to study drug or other AE of concern may, at the discretion of the Investigator (and/or medical monitor), have additional blood samples taken for safety laboratory tests.

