7.6.4.3 Tertiary Endpoints and Analysis

Analyses of tertiary endpoints will follow the same methods as the primary analyses of the primary endpoint, where data are available. The tertiary clinical efficacy analyses will assess the change from baseline for the SA-ER group compared to the placebo group using GEE for the following endpoints:

- UEC score based on percent predicted bilateral strength recorded in the upper extremity muscle groups
- LEC score based on percent predicted bilateral strength recorded in the upper extremity muscle groups
- Muscle strength (total force in kg) for each individual muscle group comprising the UEC and LEC
- Percent predicted muscle strength for each individual muscle group comprising the UEC and LEC using published normative data adjusted for age, gender, and weight
- Percent of predicted muscle strength in the knee extensors using published normative data adjusted for age, gender, and weight
- GNEM-FAS total score
- GNEM-FAS self-care domain score

- Health-related quality of life as measured by the INQoL, which will be reported as subscale scores with higher scores associated with more significantly diminished quality of life
- CGI-I scores
- CK levels in serum
- Trough (pre-dose) SA levels in serum (free) and urine (free, total, and bound; corrected for creatinine)

Additional details on the analysis of tertiary endpoints will be described in the SAP.

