7.6.5 Analyses of Drug Concentration Measurements

The SA analysis set will be used to evaluate free serum SA levels and urine SA levels (free, bound and total; corrected for creatinine) at trough (pre-dose). Changes from baseline will be analyzed using repeated measures analysis. The comparison will be between the SA-ER treatment group and placebo group using GEE.

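### SAP 8.8.4 drops the protocol's creatinine correction for urine sialic acid and reports the bound fraction on a different scale from free and total

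*SAP*

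**What the plan says.** Protocol 7.5.3 (Drug Concentration Measurements) names one correction for all three fractions: "The free, total, and bound urine SA levels (corrected for creatinine) will be measured". Protocol 7.6.4.3 (tertiary endpoints) and 7.6.5 (analysis of drug concentrations) repeat it. In Table 7.5.5.6.1 a footnote to urine creatinine ties that analyte to Section 7.5.3.

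SAP 8.8.4 defines the fractions separately:

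- Free: "Free SA levels in urine will be expressed in micrograms of SA per ml of urine".
- Total: "Total SA levels in urine will be expressed in micrograms of SA per ml of urine".
- Bound: the difference between "total sialic acid and free sialic acid in urine corrected for total protein", with a correction for *creatine* also allowed.
- Choice between the two corrections, stated in the bound-SA bullet: "The primary correction for SA will be total protein with creatine correction only used when an alternate method is required".

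SAP 4.5 lists changes in the three urine fractions and names no correction. SAP Section 1 gives the SAP precedence over the protocol where analysis methods differ.

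**The concern.** The two documents define the same three variables differently, and neither gives a reason. Under the precedence clause the SAP version would be programmed. Three consequences follow.

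- Free and total SA become spot concentrations. They then reflect how dilute the first-morning void was as well as how much SA it carried.
- The three reported fractions no longer fit together, because two are per ml of urine and the third is per unit of protein.
- The denominator for bound SA is open. The rule refers to a need for an alternate method without saying what creates that need, and the alternate is an analyte the protocol does not list.

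These variables go into a GEE comparison of the arms. Protocol 7.4.7 also says that trough free SA in serum and urine may be used to estimate treatment compliance. Noise from dilution therefore affects a use the protocol names, although a minor one.

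**Working it through.** The plan gives no figure to reproduce, so the check is a comparison of definitions followed by short algebra.

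**Definitions side by side**

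| Fraction | Protocol 7.5.3, 7.6.4.3, 7.6.5 | SAP 8.8.4 |
|---|---|---|
| Free | per creatinine | micrograms per ml, no correction stated |
| Total | per creatinine | micrograms per ml, no correction stated |
| Bound | per creatinine | (total minus free) per total protein; *creatine* as alternate |

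All three rows differ.

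**Effect of dilution**

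Let F, T, C and P be the concentrations of free SA, total SA, creatinine and protein in one specimen. Suppose a second specimen is k times as concentrated, with the same relative composition.

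- SAP free: F becomes kF. SAP total: T becomes kT.
- Protocol free: kF / kC = F / C, unchanged. The same holds for total.
- SAP bound: (kT − kF) / kP = (T − F) / P, also unchanged.

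With k = 1.5 (assumption), uncorrected free and total SA rise by 1.5 − 1 = 50%. With k = 2 they rise by 2 − 1 = 100%. The creatinine ratios do not move. The documents give no value for k, so this range is only illustrative.

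**Do the fractions add up?**

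- Protocol: T/C − F/C = (T − F)/C, which is the bound value. Free plus bound equals total.
- SAP: reported total minus reported free is T − F in micrograms per ml, while reported bound is (T − F)/P. These are equal only if P happens to be 1 in its own units.

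The SAP's bound value is consistent within itself, since one divisor is applied to the whole difference. It is the set of three reported values that does not reconcile.

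**Which analytes are listed?**

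Table 7.5.5.6.1 lists creatinine under urinalysis, with the footnote to 7.5.3. It lists creatine kinase and creatinine under chemistry, and no creatine assay anywhere. Total protein appears under chemistry; urinalysis lists protein without saying whether the result is quantitative. Creatinine is the only possible denominator that the table flags for the SA measurements.

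**Scope of the rule**

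The sentence that ranks the corrections says SA, not bound SA. It stands in the bound-SA bullet, so limiting it to bound SA is the natural reading. If it were meant for all three fractions, it would contradict the free and total bullets and would still put protein where the protocol has creatinine. The conflict remains on either reading.

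**The case against.** The strongest reply is that the hierarchy is already settled. Protocol 7.6 describes its statistical text as a guide and leaves detailed methods to the SAP, and the SAP claims precedence. A difference is then permitted. That stands as far as it goes, but it only makes the SAP rule the operative one. It does not explain the change, define the trigger or settle the *creatine* wording.

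A reader might also infer more than the documents support:

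- *That correcting bound SA for protein is an error.* No passage shows this. The sponsor may have had a reason, and the point is that none is given.
- *That bound SA is no longer total minus free on any scale.* It still is, on the protein scale. Only the reported values fail to reconcile.
- *That dilution biases the treatment comparison.* Allocation is randomised and blinded, and the documents give no reason why urine concentration should differ by arm. The expected effect is mainly extra variance.
- *That the SAP deliberately chose a different analyte.* With no creatine assay listed, a slip for creatinine is much more likely. Reading it as creatinine does not remove the conflict, because creatinine would still be only a fallback, and only for bound SA.

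The low importance of the measure is also a fair objection. The rationale for Protocol Amendment 5 says urinary SA has limited use as a measure of absorption, excretion or pharmacodynamics, and SAP 8.8.4 itself treats serum free SA as the best indicator of compliance. First-morning collection is specified and the volume is recorded, but SAP 8.8.4 makes no use of the volume.

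**Conclusion.** The conflict is real and lies in the current text of both documents. Following the SAP would give free and total values that depend on dilution and depart from the protocol's stated measure, a bound value that does not reconcile with them, and a choice of denominator with no rule behind it.

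The point is minor. It touches only the drug-concentration results, which the protocol also lists as tertiary. The primary test on upper extremity strength, the three key secondary tests and the control of type I error are unaffected. The likely cost is lost precision in the urine SA comparison. Its size cannot be derived from the documents, and the 50% to 100% movement rests wholly on the assumed 1.5- to 2-fold difference in concentration between a subject's visits.

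SAP 8.8.4 also gives urine collection times (Baseline, Weeks 24 and 48) that differ from Protocol 7.5.3 (Baseline, Weeks 16, 32 and 48). This suggests that the section was not checked against the protocol, rather than that the correction was changed on purpose. That is an inference.

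**What to change.** In SAP 8.8.4:

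1. Define free, total and bound urine SA per unit creatinine, as in Protocol 7.5.3, 7.6.4.3 and 7.6.5, with bound as total minus free on that scale.
2. Change *creatine* to *creatinine*.
3. Remove the rule that makes protein the main correction with an undefined alternate. If a protein-corrected bound value is wanted, keep it as a labelled supportive analysis, give the rationale, and name the urine protein assay.
4. Confirm that creatinine is assayed in the first-morning-void specimen used for SA. The Schedule of Events footnotes describe that void separately from the urinalysis sample, and the laboratory table lists creatinine under urinalysis. The footnote there shows the intended use but does not say that the two assays share a specimen.

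The cost is a small change to SAP wording and to the derivation of three variables. No new assay should be needed if item 4 is confirmed.

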## 8.9 Safety Analyses

Analysis of safety will be performed on the safety analysis set. Blinded study data will be monitored on an ongoing basis by the clinical study team including the medical monitor and the clinical drug safety team to ensure patients' safety.

Safety will be evaluated by the incidence, frequency and severity of AEs and SAEs, including clinically significant changes from study baseline to scheduled time points in:

- Interval history
- Vital signs and weight
- Physical examination findings
- Clinical laboratory evaluations
- Suicidal ideation and behavior assessments
- Concomitant medications

All AEs will be coded using the Medical Dictionary for Regulatory Activities (MedDRA 17.1 or beyond). The incidence and frequency of treatment emergent AEs (occurred after the first dose of study drug) will be summarized by System Organ Class (SOC), Preferred Term (PT), severity, and relationship to treatment. The numbers (frequency) and incidence rates of AEs and SAEs will be summarized by treatment group. A by-subject listing will be provided

for those subjects who experience a SAE, including death, or experience an AE associated with early withdrawal from the study or study drug treatment. Each of these outputs will include tabulation by maximum severity for each SOC and preferred term. Summaries of AEs will be provided in descending order of frequency by SOC and preferred term.

Additional tables summarizing patient incidence (by preferred term) of the following will be generated:

- All AEs;
- SAEs;
- Treatment-related AEs;
- Treatment-related SAEs;
- AEs leading to the discontinuation of study drug or discontinuation of study;
- Deaths.

Separate outputs maybe be provided for subgroups defined by gender, and race (if feasible). Detailed listings for all AEs and listings and/or narratives will be provided for serious and significant AEs, deaths (with “on-study” deaths [deaths that occur before the end of safety follow-up period] identified).

### Interval History

Each interval history is intended to record any signs, symptoms, or events (i.e., falls) experienced by the subject since the prior study visit that are not related to study procedure(s) performed at prior study visits or study drug. Interval history may include exacerbation or improvement in existing medical conditions (including the clinical manifestations of GNEM) that might interfere with study participation, safety, and/or positively or negatively impact performance of functional assessments. Interval history may identify under-reported AEs. Interval history for all subjects in the safety population will be reported in a listing.

### Clinical Laboratory Parameters

Clinical laboratory data will be summarized by the type of laboratory test. The frequency and percentage of subjects who experience abnormal clinical laboratory results (i.e. outside of reference ranges) and/or clinically significant abnormalities will be presented for each clinical laboratory measurement. For each clinical laboratory measurement, descriptive statistics will be provided for study baseline and all subsequent post-treatment scheduled visits. Changes or shifts of normal/abnormal status from study baseline to the post-treatment visits will be provided.

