5.2.4 Summary of Overall Risks and Potential Benefits

Since SA is a normal body compound with native pathways for degradative metabolism and rapid renal clearance, there is no evidence or expectation of a significant safety issue with SA replacement therapy. Data from nonclinical and clinical studies to date suggest SA-ER administered alone or with SA-IR does not pose any significant safety risks that can be identified at this time. Toxicology or adverse pharmacology findings were not observed in SA-treated animals; at very high doses, osmotic diarrhea may be observed in treated dogs.

In the 48-week Phase 2 study in 47 GNEM subjects, there were no deaths or other SAEs. The majority of subjects had TEAEs that were graded as mild to moderate severity. A single subject in the 3 g/day SA-ER group discontinued due to an AE of abnormal liver enzymes; the subject was subsequently identified as having a history of elevated liver function test results. The only AE experienced by a greater proportion of SA-ER treated subjects was abnormal liver function tests (5 subjects vs. 0 in the placebo group). It is likely alanine aminotransferase (ALT) elevations resulted from skeletal muscle disease rather than from liver damage, since gamma-glutamyl transpeptidase (GGT) was generally normal and serum CK was also elevated in these subjects. The time course of abnormality and lack of dose response suggest that these results are not study drug related. Sporadic abnormal levels of aspartate aminotransferase (AST) and ALT were also reported throughout the study, irrespective of time point or treatment group.

The most common treatment-related TEAEs were GI events (diarrhea, flatulence, abdominal pain and dyspepsia), headache and fatigue. The patterns of AEs were similar in the placebo-controlled phase of the study (the first 24 weeks) and for all 48 weeks. No correlation was observed between the GI events and free SA serum levels suggesting the frequency of GI events does not appear to be dose dependent. No subjects from the Placebo group reported diarrhea or abdominal pain, or had abnormal liver function tests after crossing over to SA-ER treatment in the continuation phase of the study.

Safety results in the ongoing Phase 2 study (UX001-CL202) indicate the most common TEAE reported by subjects receiving a higher dose of 12 g/day SA-ER/SA-IR involve GI disorders, including diarrhea, flatulence, dyspepsia, and abdominal pain.

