7.3.2 Exclusion Criteria

Individuals who meet any of the following exclusion criteria will not be eligible to participate in the study:

- 1) Ingestion of N-acetyl-D-mannosamine (ManNAc), SA, or related metabolites; intravenous immunoglobulin (IVIG); or anything that can be metabolized to produce SA in the body within 60 days prior to the Screening Visit
- 2) History of more than 30 days treatment with SA-ER and/or SA-IR in prior clinical trials in the past year
- 3) Has had any hypersensitivity to SA or its excipients that, in the judgment of the investigator, places the subject at increased risk for adverse effects
- 4) Has serum transaminase (i.e. aspartate aminotransferase [AST] or gamma-glutamyl transpeptidase [GGT]) levels greater than 3X the upper limit of normal (ULN) for age/gender, or serum creatinine of greater than 2X ULN at Screening

- 5) Pregnant or breastfeeding at Screening or planning to become pregnant (self or partner) at any time during the study
- 6) Use of any investigational product or investigational medical device within 30 days prior to Screening, or anticipated requirement for any investigational agent prior to completion of all scheduled study assessments
- 7) Has a condition of such severity and acuity, in the opinion of the investigator, that it warrants immediate surgical intervention or other treatment or may not allow safe participation in the study
- 8) Has a concurrent disease, active suicidal ideation, or other condition that, in the view of the investigator, places the subject at high risk of poor treatment compliance or of not completing the study, or would interfere with study participation or would affect safety

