8.5.4 Adverse Event Reporting

8.5.4.1 General

All AEs (i.e. any new or worsening in severity or frequency of a preexisting condition) with onset after the subject signs consent for study participation must be promptly documented on the CRF. The Principal Investigator is responsible for evaluating all AEs, obtaining supporting documents, and ensuring documentation of the event is adequate. Details of the AE must include severity, relationship to study drug, duration, and outcome.

All AEs will be collected from the time the subject signs the informed consent through 30 days following the last dose of study drug, or, if applicable, until the date the subject signs

the informed consent for the open-label extension study, UX001-CL302, whichever occurs sooner. In addition for those subjects choosing not to enroll in UX001-CL302, the Investigator should report any AE that occurs more than 30 days following the last dose of study drug that is believed to have a reasonable possibility of being associated with study drug.

AEs ongoing after the defined follow-up period stated in the paragraph above should have a comment in the source document by the Investigator that the event has recovered, recovered with sequelae, or stabilized.

8.5.4.2 Serious Adverse Events, Serious Adverse Drug Reactions, and Requirements for Immediate Reporting

Ultragenyx or its designee must be notified of the occurrence of any SAE that occurs during the reporting period within 24 hours of the Investigator, designee, or site personnel's knowledge of the event. SAEs will be reported by completing and submitting SAE report forms to Ultragenyx or designee.

Follow-up SAE information must be submitted in a timely manner as additional information becomes available. All SAEs regardless of relationship to study drug must be followed to resolution or stabilization if improvement is not expected.

All deaths, regardless of causality, occurring from signing of the informed consent through the defined follow-up period stated in Section 8.5.4.1 are to be reported as SAEs to Ultragenyx or its designee within 24 hours of knowledge.

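### Low-priority improvement: the planned laboratory range count and normal/abnormal shift cannot separate a further ALT or AST rise from no change in a subject already above range at baseline; adding a worst-value shift in multiples of ULN by arm would close most of that gap

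*SAP*

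**What the plan says.** **Planned laboratory outputs.** SAP 8.9 (Clinical Laboratory Parameters) plans three outputs for each test:
- a frequency and percentage of subjects, in that "abnormal clinical laboratory results (i.e. outside of reference ranges) and/or clinically significant abnormalities will be presented for each clinical laboratory measurement";
- descriptive statistics at baseline and at each scheduled visit;
- a baseline comparison, in that "Changes or shifts of normal/abnormal status from study baseline to the post-treatment visits will be provided".

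Protocol 7.6.6 also plans changes from baseline to post-treatment visits. SAP 8.1 includes maxima among the summary statistics and provides for data listings.

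**Entry limits.** Exclusion 4 (Protocol 7.3.2) excludes AST or GGT "levels greater than 3X the upper limit of normal (ULN) for age/gender". ALT is not named.

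**Adverse-event route.** Protocol 8.5.4.1 counts as an AE "any new or worsening in severity or frequency of a preexisting condition". Protocol 7.5.5.10 has clinically significant laboratory changes recorded as AEs where appropriate, and Protocol 8.5.2 grades AEs by CTCAE 4.03 where possible. SAP 8.9 tabulates AEs by maximum severity. SAP 8.9.1 and Appendix 10.6.2 give liver-related preferred terms their own incidence table.

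**Phase 2 background (Protocol 5.2.4).** The only AE reported in a greater proportion of SA-ER subjects was "abnormal liver function tests (5 subjects vs. 0 in the placebo group". One subject, on 3 g/day, discontinued for abnormal liver enzymes; "the subject was subsequently identified as having a history of elevated liver function test results". Sporadic AST and ALT abnormalities "were also reported throughout the study, irrespective of time point or treatment group". The protocol thinks muscle the likely source of the ALT elevations, "since gamma-glutamyl transpeptidase (GGT) was generally normal and serum CK was also elevated in these subjects". It also reports no dose response, and no abnormal liver tests in placebo subjects after they crossed over to SA-ER.

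**The concern.** A two-state classification carries no information about size once a subject is in the abnormal state. In most trials few subjects start there, so little is lost. Here an above-range start is realistic. Eligibility permits it, the disease can itself raise transaminases, sporadic abnormalities occurred in every Phase 2 group, and the one liver-enzyme discontinuation was in a subject with such a history.

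What is at stake is limited to how one safety question is described. Liver tests are the one AE the protocol singles out as more frequent on SA-ER in Phase 2, and it offers muscle as the likely explanation. A 48-week randomized placebo arm is a good setting in which to check that explanation with measured values. The two planned categorical laboratory summaries cannot do so for subjects who enter above range.

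**Working it through.** The plan states no figure on this point, so there is nothing to reproduce. The check applies the planned rules and a banded rule to the same pairs of values.

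**Rules**
- Out-of-range count: 1 if any post-baseline value exceeds ULN.
- Normal/abnormal shift: change of state, 0 if the state is the same at baseline and afterwards.
- Banded shift (example bands, an assumption): up to 1, >1–3, >3–5, >5–10, >10 × ULN; the result is the number of bands moved from baseline to worst value.
- Listing rule: worst ALT or AST above 3 × ULN and above the subject's own baseline.

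**Cases (× ULN, baseline to worst)**

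| Case | Fold of baseline | Range count | Shift | Bands moved | Listed |
|---|---|---|---|---|---|
| AST 2.9 to 2.9 | 1.00 | 1 | 0 | 0 | no |
| AST 2.9 to 5.5 | 5.5/2.9 = 1.90 | 1 | 0 | +2 | yes |
| AST 2.9 to 8 | 8/2.9 = 2.76 | 1 | 0 | +2 | yes |
| ALT 4 to 12 | 12/4 = 3.00 | 1 | 0 | +2 | yes |
| 1.1 to 2.9 | 2.9/1.1 = 2.64 | 1 | 0 | 0 | no |
| 2.9 to 3.1 | 3.1/2.9 = 1.07 | 1 | 0 | +1 | yes |

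The range count and the shift are the same in every row. The banded shift separates the three large rises from no change. The last two rows show its band-edge errors: it misses a 2.64-fold rise and flags a 7% one.

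**Arm-level illustration (all inputs assumed except about 40 per arm).** Suppose 40% of each arm, 0.40 × 40 = 16 subjects, start at 1.5 × ULN. Five SA-ER subjects rise to 6 × ULN and nobody else changes.
- Out of range: 16/40 in both arms.
- Abnormal-to-abnormal: 16 in both arms.
- Banded shift: 5 versus 0 subjects move from >1–3 to >5–10 × ULN.
- Mean change: 5 × (6 − 1.5)/40 = 0.56 × ULN versus 0. This differs between arms, but does not say how many subjects rose or how far.

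The number of subjects in whom these two outputs could not show a further rise depends on the unreported share above range at baseline. An assumed 10% to 60% gives 4 to 24 of 40 per arm.

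**How much weight 5 versus 0 can bear.** Denominators are not given. If the 47 Phase 2 subjects split about 31 SA-ER to 16 placebo, the chance that all five cases fall on SA-ER with no drug effect is C(31,5)/C(47,5) = 0.11. For 29 or 33 on SA-ER it is 0.08 or 0.15. None of these figures allows for unequal exposure time.

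**Sparseness.** Five by five bands give 25 cells per analyte; 40/25 = 1.6 subjects per cell on average.

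**The case against.** The strongest reply is that the two outputs should not be judged alone. SAP 8.9 evaluates clinically significant changes from baseline in laboratory tests. The protocol plans numeric changes from baseline. Maxima and listings would show an extreme value. A meaningful rise should also become a graded AE and reach the liver table. All of that stands, and a reader who inferred that the plan is blind to such rises would be wrong. What these outputs do not give is a count of subjects by arm by size of measured rise. Means and maxima are group-level. The clinically significant category has no stated threshold. AE grades depend on an investigator choosing to report a rise that, in this disease, is easily put down to muscle.

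A second reply is that the liver background is thin, and this also stands. Besides the chance figures above, the protocol reports no dose response and no cases after placebo crossover, and the discontinuation was at half the dose tested here. A reader might infer that SA-ER has an established liver signal. The documents do not support that, and this point does not need it; the added table could equally support the muscle explanation.

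A third reply concerns the remedy. Protocol 7.5.5.6 allows extra blood samples at the investigator's discretion after a related SAE or other AE of concern. A worst value over all draws tends to rise with the number of draws, so it could bring AE-driven sampling back into the comparison. A worst-value table also loses timing and below-range values. Both criticisms are right. They are reasons to add the table without replacing the planned shift, and to base the main comparison on protocol-timed samples.

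**Conclusion.** The point holds as a cheap, optional improvement of low priority. For a subject already above range at baseline, the planned range count and normal/abnormal shift return the same result whatever the later rise in ALT or AST. The other planned outputs cover this in part, but none counts subjects by arm by size of measured rise without relying on investigator reporting.

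No rate or probability of a missed finding is claimed. The conclusion rests on the wording of the SAP and of Exclusion 4, and on the protocol's own account that transaminase abnormalities occur in this population. The bands are illustrative, and the arm-level example and the Phase 2 split are assumptions. It would go too far to read this as an error in the plan, as evidence of liver toxicity, or as a threat to the primary inference, error control or subject protection.

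**What to change.** In SAP 8.9, before unblinding, keep all planned outputs and add two items.

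1. **Shift table by arm** for ALT, AST, GGT, bilirubin and alkaline phosphatase, from baseline category to worst post-baseline category in multiples of ULN (for example up to 1, >1–3, >3–5, >5–10, >10). Base the by-arm comparison on scheduled and early-termination samples, then repeat it with unscheduled samples included. State that the rule in SAP 8.2 preferring the scheduled value within a visit window does not apply to this worst value; otherwise an early-termination or unscheduled peak could be dropped.
2. **Listing by arm** of subjects whose worst ALT or AST exceeds both 3 × ULN and their own baseline, giving the baseline value, fold of baseline, and same-visit GGT, bilirubin and CK. This lets the muscle explanation be examined subject by subject.

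State that the cut-offs are for reporting only and imply no treatment decision.

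**Cost.** SAP wording, one table and one listing. No new sample is needed: these analytes and CK are in the chemistry panel (Protocol 7.5.5.6), already planned 8 times per subject (Protocol 7.5.5.6.1).

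**Downsides.** Some programming, sparse cells and the band-edge effects shown above, so the table must be read alongside the planned changes from baseline.
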